3.4.2 Secondary Efficacy Endpoints

Similar MMRM models as described for the primary analyses will be used to analyze the secondary efficacy endpoints. In order to maintain the overall Type 1 error rate, the secondary efficacy endpoints will be tested sequentially at the 0.05 significance level according to the order of hierarchy specified below:

- Percent change from Day 1 to Day 84 in LDL-C for the obicetrapib monotherapy treatment group compared with the placebo group;
- Percent change from Day 1 to Day 84 in ApoB for the combination treatment group compared with the placebo group; and

- Percent change from Day 1 to Day 84 in ApoB for the obicetrapib monotherapy treatment group compared to the placebo group.

3.4.3 Exploratory Efficacy Endpoints

Similar MMRM models as described for the primary analyses will be used to assess the percent change from Day 1 to Day 84 in non-HDL-C, VLDL-C, HDL-C, TG, ApoE and Lp(a).

The proportion of participants at Day 84 that achieve LDL-C <2.6 mmol/L (<100 mg/dL), LDL-C <1.8 mmol/L (<70 mg/dL), and LDL-C <1.4 mmol/L (<55 mg/dL) will be examined through Logistic Regression Models with covariates of treatment group and the baseline LDL-C value.

The Logistic Regression Model will be implemented using SAS® Proc LOGISTIC. The sample SAS code can be found below:

```
*****
Note:
USUBJID = unique subject identifier
TREATMENT = = 0 (Placebo), 1 (Obicetrapib monotherapy), 2 (Combination therapy)
BASE = Baseline value
LDLC100 = LDL_C value less than 100mg/dL at DAY84 (YES/NO) for example
*****
proc logistic data= LDL_C;
  Class TREATMENT(ref=0) / Param= Ref;
  Model LDLC100= TREATMENT BASE / alpha=0.05 expb plcl plrl orpvalue lackfit;
  Ods output
    ParameterEstimates= Log_LDLC100_ParameterEstimates
    CLoddsPL= Log_LDLC100_OddsRatios
    ;
Run;
*****
```

Similar ANCOVA models as described in the secondary sensitivity analysis for the primary analyses will be used to assess the percent change from Day 1 to Day 84 in HDL particles (total), IDL particles, LDL particles (total), VLDL/Chylomicron particles and PCSK9.

No adjustments will be made for multiplicity in testing the exploratory endpoints. Nominal p-values will be provided.

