## 9.2.1.3 Exploratory analyses

Similar MMRM models will be used for the percent change from Day 1 to Day 84 in non-HDL-C, VLDL-C, HDL-C, TG, ApoE, Lp(a), and HDL-ApoE.

The proportion of participants at Day 84 that achieve LDL-C <2.6 mmol/L (<100 mg/dL), LDL-C <1.8 mmol/L (<70 mg/dL), and LDL-C <1.3 mmol/L (<50 mg/dL) will be examined through logistic regression models for binary variables with covariants of the treatment groups and the baseline variable.

No adjustment will be made for multiplicity in testing the exploratory efficacy endpoints. Nominal p-values will be provided when applicable. Any additional sensitivity and/or supplemental analyses will be defined in the SAP.

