3.1.4 Summary Statistics

Categorical data will generally be summarized with counts and percentages of participants. The denominator used for the percentage calculation will be clearly defined. Continuous data will generally be summarized with descriptive statistics including n (number of non-missing values), mean, median, standard deviation, minimum, and maximum.

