6 PROGRAMMING SPECIFICATIONS

Analyses will be performed using SAS® version 9.4 or higher. All available data will be presented in subject data listings which will be sorted by subject and visit date as applicable. Detailed Programming Specifications will be provided in a separate document.

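### SAP 3.4.3 has no method for an arm with no or all responders in the LDL-C target logistic models, a likely outcome at the planning SD under assumed baselines and a flat placebo arm

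*SAP*

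**What the plan says.** SAP 3.4.3 covers the three Day 84 LDL-C targets with one model form. For the lowest target: "LDL-C <1.4 mmol/L (<55 mg/dL) will be examined through Logistic Regression Models with covariates of treatment group and the baseline LDL-C value". The sample code sets placebo as the reference level and uses "Model LDLC100= TREATMENT BASE / alpha=0.05 expb plcl plrl orpvalue lackfit". That is ordinary maximum likelihood with profile-likelihood limits. It has no Firth option and no exact statement. Two tables are saved: "ParameterEstimates= Log_LDLC100_ParameterEstimates" and "CLoddsPL= Log_LDLC100_OddsRatios".

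On p-values the SAP says only "Nominal p-values will be provided", without naming the test. Protocol 9.2.1.3 is more guarded: "Nominal p-values will be provided when applicable". Neither that section nor SAP section 5, which moves the lowest threshold from 50 to 55 mg/dL, adds a fallback.

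Two other statements bear on the point. SAP 3.1.4 says "Categorical data will generally be summarized with counts and percentages of participants", and SAP section 6 says "Detailed Programming Specifications will be provided in a separate document". That separate document is not available here.

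**The concern.** If an arm has no responders, or only responders, the likelihood for that arm's coefficient has no maximum. The estimate runs off to infinity and its standard error grows faster. The Wald statistic shrinks towards zero, and its value depends on where the software stops iterating.

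The design points towards this. Participants enter above 70 mg/dL on a stable statin, so few on placebo should be below 55 twelve weeks later. Large falls are expected on active treatment, so all of a combination arm of about 36 may be below 100.

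The damage depends on which arm is affected. Because placebo is the reference, 0/36 on placebo removes both active-versus-placebo odds ratios. If only the combination arm is full, the combination odds ratio is lost and the monotherapy one survives. If the Wald value were then reported as the nominal p-value, it would look null beside a very large difference in responders. The choice of another method would have to be made after unblinding.

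**Working it through.** **The plan's own figures.** SAP 2.2.2 gives a 30-point difference, SD 15 points, 36 evaluable per arm, 1-sided 0.025 and about 5% dropout. The standard error is 15 × √(2/36) = 3.54. Then 30/3.54 = 8.49, and 8.49 − 1.96 = 6.53, so power exceeds 0.9999 and the stated >90% is met. Enrolment: 108/0.95 = 113.7, hence 114, or 38 per arm.

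**Why an all-or-none arm is foreseeable.** Take Day 84 LDL-C = baseline × (1 + change), with change Normal and SD 15 points. For a flat placebo participant to be below 55:
- baseline 70: change below 55/70 − 1 = −21.4%, z = −1.43, probability 0.077;
- baseline 100: change below −45%, z = −3, probability 0.0013.

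With arm-average response probability p, P(no responder) = (1 − p)^36 and P(all respond) = p^36. For baselines uniform on 70-130:
- placebo <55: p = 0.009, 0.991^36 = 0.72;
- active at −30%, <100: p = 0.926, 0.926^36 = 0.063.

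Across seven assumed baseline distributions, all above 70, P(no placebo responder <55) ran from 0.31 to 0.84. At least one of the three models was affected with probability 0.63 or more in every one.

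**Fuller simulation.** 20,000 trials per scenario, 36 per arm. Assumed screening LDL-C: mean 90, 100 or 110, SD 20 or 30, truncated at >70. The floor applies at screening only (Protocol 4.1), while baseline is the last pre-dose value (SAP 3.1.3), so a screening-to-Day-1 CV of 0, 10 or 15% was added.

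Effects (monotherapy/combination) are the planning −30/−30 and two pairs built from Protocol 1.3 and 1.4.1 by compounding with the 15.1% ezetimibe effect:
- 1 − (1 − 0.454)(1 − 0.151) = 53.6%;
- 1 − (1 − 0.503)(1 − 0.151) = 57.8%.

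Where placebo falls 5%, the planning pair becomes −35/−35 to keep the 30-point difference. The other pairs are falls from baseline and are unchanged.

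P(at least one all-or-none arm in any of the three models), %, range over baseline settings:

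| SD | Placebo | CV | −30/−30 | −45.4/−53.6 | −50.3/−57.8 |
|---|---|---|---|---|---|
| 15 | flat | 0-10% | 58-90 | 83-99 | 89-100 |
| 15 | flat | 15% | 38-65 | 70-94 | 79-98 |
| 15 | −5% | 0-10% | 43-79 | 73-99 | 82-100 |
| 15 | −5% | 15% | 26-49 | 59-93 | 71-97 |
| 20 | flat | 0-10% | 28-61 | 55-90 | 62-96 |
| 20 | −5% | 15% | 10-25 | 31-72 | 40-85 |

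For the first row:
- the <100 model separates more often than the <55 model in 0, 6 and 10 of the 12 settings for the three effect pairs in order;
- the <70 model is affected in 1-28%;
- the combination odds ratio is lost in at least one model in 57-90%, 81-98% and 87-99%;
- the monotherapy odds ratio is lost in at least one model in 57-89%, 70-92% and 77-96%.

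**Worked dataset.** One simulated trial: baseline mean 100, SD 25, CV 10%, percent-change SD 15, changes 0/−45.4/−53.6. Responders on placebo, monotherapy and combination were 0, 14 and 24 of 36 for <55, and 19, 34 and 36 of 36 for <100. Combination versus placebo:

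| | <55 | <100 |
|---|---|---|
| Wald p at iteration 8, 12, 25 | 0.53, 0.91, 0.9997 | 0.49, 0.90, 0.9997 |
| Profile-likelihood interval for OR | 43 to infinity | 36 to infinity |
| Firth OR (95% CI) | 186 (22 to 24,500) | 172 (15 to 26,800) |
| Penalised likelihood-ratio p | 2e-11 | 3e-8 |
| Risk difference (Newcombe 95% CI) | 67% (48% to 80%) | 47% (29% to 63%) |

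The ordinary likelihood-ratio p for <55 is 3e-12. In the <100 model monotherapy stays estimable (Wald p 0.0006). The iteration figures come from a Newton-Raphson fit and show the mechanism; they are not PROC LOGISTIC output.

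**The case against.** The strongest reply is that little is at risk. The endpoints are exploratory, and the primary and secondary analyses do not use these models. The SAP does not say that the Wald p-value will be the one reported: the code also requests an odds-ratio p-value and saves the profile-likelihood table, the protocol promises p-values only where applicable, and the detailed specifications are separate. The planned profile limits exclude 1 in the worked example, and 0/36 against 24/36 would be plain from the counts. All of this stands, and it is why the point is minor.

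The frequencies can also be questioned. They rest on an assumed baseline, CV and placebo change, and they pool three models. At the planning effect with CV 15% they fall below one half in some settings even at SD 15% with a flat placebo. At SD 25% and the planning effect, a smaller run (4,000 trials per setting) gives 9-28% with flat placebo and CV 0-10%, and 3-9% with placebo −5% and CV 15%. The planning case is mainly a <55 problem. The larger effects come from mild dyslipidemia, one of them on top of atorvastatin 20 mg, and the documents state no combination effect. These limits also stand. They bear on how often separation occurs, not on what the stated method gives when it does.

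Finally, a fallback rule could replace Firth for all three targets, since <70 is usually estimable. One pre-specified model for all three is sounder than a switch triggered by the data.

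**Conclusion.** The concern holds, as a minor one. Followed as written, SAP 3.4.3 gives no finite odds ratio and an uninformative Wald p-value whenever an arm has no or all responders, and it names neither a fallback nor the source of the nominal p-value.

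At SD 15% with a flat placebo arm, CV 0-10% and the assumed baselines, that outcome is more likely than not in at least one model. The model most exposed is <55 at the planning effect and often <100 at the larger cited effects. The likelihood drops with a larger SD, a fall on placebo, or more screening-to-Day-1 variation. No confirmatory conclusion is affected.

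**What to change.** In SAP 3.4.3:
- add `FIRTH` to the MODEL statement for all three targets and keep the profile-likelihood limits already requested;
- state that nominal p-values come from the penalised likelihood-ratio test, not the Wald test;
- report, beside the planned counts and percentages, the risk difference with 95% CI for each active arm versus placebo.

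The cost is one model option, one sentence, a reduced-model fit per comparison, and one risk-difference line per target. The downside is slight shrinkage of the odds ratios. Their intervals also stay very wide when an arm has no or all responders (22 to 24,500 in the example), so the risk difference, which is not adjusted for baseline, would be the more readable figure.

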2.3.3 Exploratory Efficacy Endpoints

The exploratory efficacy endpoints include the following:

- Percent change from Day 1 to Day 84 in non-HDL, VLDL-C, HDL-C, TG, ApoE, Lp(a), and HDL-APOE for the obicetrapib 10 mg + ezetimibe 10 mg combination treatment group compared with the placebo group and for the obicetrapib 10 mg monotherapy group compared with the placebo group;
- Proportion of participants at Day 84 that achieve LDL-C $<$ 2.6 mmol/L ($<$ 100 mg/dL), LDL-C $<$ 1.8 mmol/L ($<$ 70 mg/dL), and LDL-C $<$ 1.4 mmol/L ($<$ 55 mg/dL) for the obicetrapib 10 mg + ezetimibe combination treatment group compared with the placebo group and for the obicetrapib 10 mg monotherapy treatment group compared with the placebo group;
- Percent change from Day 1 to Day 84 in HDL particles (total), IDL particles, LDL particles (total) and VLDL/Chylomicron particles for the obicetrapib 10 mg + ezetimibe 10 mg combination treatment group compared with the placebo group and for the obicetrapib 10 mg monotherapy group compared with the placebo group; and
- Percent change from Day 1 to Day 84 in PCSK9 for the obicetrapib 10 mg + ezetimibe 10 mg combination treatment group compared with the placebo group and for the obicetrapib 10 mg monotherapy group compared with the placebo group.

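### The sample PROC LOGISTIC code for LDL-C target attainment does not name the modelled response level; run as printed, it gives odds ratios for missing the target

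*SAP*

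**What the plan says.** SAP 2.3.3 words the endpoint as attainment: "Proportion of participants at Day 84 that achieve LDL-C" below each threshold. SAP 3.4.3 repeats this for <100, <70 and <55 mg/dL and names logistic regression with treatment group and baseline LDL-C as covariates.

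The code in SAP 3.4.3 is introduced with "The sample SAS code can be found below". Its parts are:

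- Response: "LDLC100 = LDL_C value less than 100mg/dL at DAY84 (YES/NO) for example". YES therefore means the target was reached.
- Procedure call: "proc logistic data= LDL_C", with no DESCENDING or ORDER= option.
- Model: "Model LDLC100= TREATMENT BASE / alpha=0.05 expb plcl plrl orpvalue lackfit". The response carries no EVENT=, REF= or DESCENDING option.
- Treatment: "Class TREATMENT(ref=0) / Param= Ref". This makes placebo the comparator arm and does not touch the response.
- Output: "CLoddsPL= Log_LDLC100_OddsRatios". The odds ratios are saved directly, with no inversion step.

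SAP section 6 leaves detailed programming specifications to a separate document. SAP 3.4.3 makes no multiplicity adjustment for the exploratory endpoints and gives nominal p-values.

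**The concern.** The text asks about reaching a target, while the code leaves the modelled outcome to a software default. If that default picks the opposite level, an arm that brings more participants to target shows an odds ratio below 1. A reader who takes the endpoint wording at face value would read that as harm.

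These endpoints carry only nominal p-values, so the size and direction of the odds ratio are most of what the models deliver. The p-value gives no warning, because it is the same in both directions. A second programmer who works from the same sample code could repeat the reversal, so double programming need not catch it.

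**Working it through.** The plan states no attainment rate or odds ratio for this endpoint, so there is no figure of its own to reproduce. The check sets the code against the endpoint text and then works out the consequence.

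**Inputs.** The endpoint direction, response coding and code options are those listed above, from SAP 2.3.3 and 3.4.3. One input comes from outside the documents: the default of PROC LOGISTIC, which for a binary response with no event named models the first level in ascending order.

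**Step 1: which level is modelled.**

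| Stored values | First in order | Outcome modelled |
|---|---|---|
| NO, YES | NO | target not reached |
| N, Y | N | target not reached |
| 0, 1 (1 = reached) | 0 | target not reached |
| 1 = reached, 2 = not reached, no format | 1 | target reached |

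Only the last coding gives the intended direction, and the SAP does not define it.

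**Step 2: what this does to the estimates.** Let p be the probability of reaching the target, with

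logit(p) = a + b_k + c × BASE,

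where b_k is the effect of active arm k against placebo. The odds ratio for reaching the target is exp(b_k). Since logit(1 − p) = −logit(p), the model for missing the target is

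logit(1 − p) = −a − b_k − c × BASE,

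so:

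- the odds ratio becomes exp(−b_k) = 1 / exp(b_k);
- limits (L, U) become (1/U, 1/L). This also holds for profile-likelihood limits, because the likelihood is the same with the signs reversed;
- the test statistic keeps its magnitude and the p-value is unchanged;
- the baseline odds ratio is inverted too.

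**Step 3: numerical check of the identity.** The SAP's model form, with baseline as covariate, was fitted both ways to one simulated data set at the <70 mg/dL threshold. It had 36 participants per group and SD 15 points. The mean changes were assumed to be 0, −30 and −45% for placebo, monotherapy and combination. The baseline was assumed normal with mean 100 and SD 22 mg/dL, with values below 71 set to 71. Limits are 95% Wald limits. The values show the reversal only and do not forecast the trial.

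| Term | Event = reached | Event = not reached | Check |
|---|---|---|---|
| Monotherapy | 18.02 (4.15 to 78.3) | 0.0555 (0.0128 to 0.241) | 1/18.02 = 0.0555; 1/78.3 = 0.0128; 1/4.15 = 0.241 |
| Combination | 84.5 (15.0 to 476) | 0.0118 (0.0021 to 0.0667) | 1/84.5 = 0.0118; 1/476 = 0.0021; 1/15.0 = 0.0667 |
| Baseline, per mg/dL | 0.921 | 1.086 | 1/0.921 = 1.086 |

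The p-values were identical in the two fits.

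**Step 4: how much is affected.** 3 targets × 2 active arms = 6 treatment odds ratios, plus 3 baseline odds ratios.

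**Step 5: whether another section settles the direction.** None does. Protocol 9.2.1.3 and SAP 2.3.3, 3.4.3 and 5 never name the modelled level. Elsewhere the SAP does use example code to fix direction: the ANCOVA code for Sensitivity Analysis 2 labels its contrast as combination minus placebo and gives the coefficients.

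**The case against.** The strongest reply is that this is sample code. Detailed specifications sit in a separate document that is not available here, and the final programs may name the event. Other sample code in the SAP is also incomplete: the PROC MIXED block has no input data set and no output statement, yet later code uses data sets that it would have to create. The YES/NO note describes a variable and does not fix its stored values. All of this stands. A reader might infer that every odds ratio the trial reports is inverted. The documents do not support that, because they show only what happens if the code is run as printed with one of the usual codings.

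A second reply is that the reversal would be noticed. SAP 3.1.4 summarises categorical data by counts and percentages, and a higher active-arm percentage beside an odds ratio below 1 is an evident conflict. The baseline odds ratio would also point the wrong way, and SAP 4.3 has comments on the pre-final output resolved before the final analysis. This makes detection likely but does not assure it.

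A third reply is that an odds ratio for non-attainment is a legitimate summary with the same test. That is true if it is labelled so, and nothing in the SAP labels it so. The output data set names identify the threshold and not the modelled level, so they neither cause nor correct a misreading.

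**Conclusion.** Wrong as written, and limited to exploratory endpoints. Run as printed with YES/NO, N/Y or 0/1 coding, the code returns the odds ratio for missing each LDL-C target, which is the reciprocal of what the endpoint text calls for. This rests on the default ordering of PROC LOGISTIC and on the code being used without change.

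The size of the error is exactly 1/x for whatever odds ratio the data give. A reader might want a predicted value. The documents give neither attainment rates nor a baseline LDL-C distribution, and any such value would also have to come from the baseline-adjusted model, so none is offered.

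It would also be too strong to call the analysis invalid. The model, covariates, comparator arm, p-values, attainment percentages, type I error and the primary and secondary analyses are unaffected. What is wrong is the direction and labelling of the estimates.

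**What to change.** In SAP 3.4.3, name the event on the response: `Model LDLC100(event='YES') = TREATMENT BASE / ...`. Do the same for the <70 and <55 mg/dL responses. If the stored values are not YES and NO, name the value that means the target was reached.

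Add one sentence to the text: odds ratios above 1 mean that more participants reach the target than on placebo. Carry both changes into the programming specifications. If those already name the event, bring the SAP into line with them.

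The cost is one option in each of three model statements and one sentence. No data collection, sample size or inference changes.

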3.5 Pharmacokinetic Assessment

Plasma obicetrapib concentrations will be summarized with descriptive statistics based on the PK Population. Exploration of any relationships with obicetrapib exposure will be performed, as appropriate.

3.6 Safety Assessment

The Safety Population will be the primary population for the safety analyses. All safety endpoints will be summarized descriptively by treatment group and overall. No statistical inference will be applied to the safety endpoints.

3.6.1 Adverse Events (AEs)

AEs will be categorized by primary system organ class and preferred term as coded using the MedDRA (version 24.1) category designations.

An overview of treatment-emergent AEs (TEAEs) will be provided including counts and percentages of participants (and event counts) with the following:

- Any TEAEs overall and by maximum severity
- Any study drug related TEAEs, overall and by maximum severity
- Any TEAEs leading to discontinuation of study drug
- Any treatment-emergent serious AEs (TESAEs)
- Any study drug related TESAEs
- Any TEAEs leading to death

The TEAEs described above will be summarized separately by System Organ Class and Preferred Term.

Listings will be presented specifically for TEAEs, TESAEs and TEAEs leading to discontinuation of study drug.

3.6.2 *Clinical Laboratory Tests*

Blood for chemistry and hematology will be obtained as indicated in Table 1 Schedule of Procedures and sent to a central laboratory for analysis. See Appendix A for a complete list of analytes. Blood samples for chemistry and hematology must be obtained under fasting conditions (i.e., after the participant has fasted for ≥ 10 hours).

Laboratory values will be summarized descriptively, including the change and percent change from baseline. In addition, shift tables will be presented to describe the change in laboratory parameter values at post-baseline visits using normal range categories (low, normal, and high).

All safety laboratory data will be presented in participants listings.

3.6.3 *Vital Signs*

Vital signs including body temperature, heart rate, and triplicate blood pressure will be measured at all scheduled visits. Triplicate blood pressure measurements will be averaged for analysis.

Values and changes from baseline will be summarized with descriptive statistics at each visit.

Separate plots will be provided for the change from baseline in systolic and diastolic blood pressure by visit.

Height and weight will be measured at the Screening Visit only. Body Mass Index (BMI) will be derived as weight/(height/100)² (kg/m²); rounded and displayed to 1 decimal place.

3.6.4 *Electrocardiograms*

A single, standard 12-lead ECG will be performed on-site at the Screening Visit and read locally.

ECG data will be summarized with descriptive statistics and presented in participant listings.

3.6.5 *Physical Examinations*

Physical examinations will be performed at the Screening Visit and at Day 84. Data collected related to physical examinations will be listed.

